## 9.2 Recruitment and consent

Patients are informed about the study at the end of the intake by the intake therapist or research assistant. Patients that are eligible for individuale treatment will receive the study information through mail and are contacted a week later by one of the research assistants or the researcher. On the phone they are asked if they have questions about the study and if they are willing to participate. If they are willing to participate the diagnostic interview is scheduled. This is usually planned one or two weeks in advance. At the beginning of the diagnostic interview, the consent form is signed by tht patient.

#### 9.3 Benefits and risks assessment

The purpose of this study is to test a feedback system for therapists, with which they will be able to identify patients that are at risk for treatment failure earlier in treatment. From the studies of Michael Lambert, it has been shown that outcomes are greatly improved for the at risk patients when the feedback is used. So the potential benefit is that at risk patients (approximately 25%) are identified earlier and might receive better care. The risks of participating in the study are minimal. Patients are interviewed once and complete questionnaires, with a maximum of 17 times. The maximum time investment of the patient is 5 hours in total. Patients might experience unpleasant feelings while completing the questionnaires or while participating in the interview. These feelings can be addressed in treatment. If a patient experiences a great amount of distress during the diagnostic interview and needs to see a therapist directly, the psychiatric nurse from the crisis team that is on call at that moment, can always be asked to see the patient directly and the psychiatrist that is on call can be consulted as well.

## **10. ADMINISTRATIVE ASPECTS AND PUBLICATION**

#### 10.1 Handling and storage of data and documents

Most of the data is collected through the web-based software RequestXL, which is hosted online through a secure server. For the study, a specific module has been build, that is not available in the current program. Therapists, patients, researchers and research assistants are given access to relevant parts of the program by the principal investigator:

- Patients can only log into the program for completing the OQ-45 and ASC. After completing the questionnaire, they are logged out automatically. They cannot access any data or scores.
- Therapists have access to their own patients, but not those of other therapists. They can log in to view the feedback (if the patient is in one of the two feedback conditions) and to complete their questionnaires.
- Research assistants have access to all patients in their own research location. They can add new patients, erase patients and adapt patient information (not questionnaires).
- The principal investigator has access to all patients in the study, at all research locations and is the only person that can export the data. After study termination the data stored in Request XL will be cleared and deleted.

Data is exported to an Excel file and will be imported into SPSS. The data file contains patient number (which offers the opportunity to match the data with patient file data (e.g. diagnosis), but patient name, date of birth and other personal details that may identify the patient are removed. After matching the data the patient number will be removed. Data is stored on the server of GGZ Noord-Holland-Noord. After the study, the datafile is kept for 20 years, for the purpose of future data analysis.

The MINIPlus is administered through QuestManager, the questionnaire system that is used by the collaborating mental health care institutions in the SynQuest collaboration (GGZ Noord-Holland-Noord, Dimence, Rivierduinen, Reinier van Arkel groep, GGZ Breburg, GGZ Delfland, LUMC). Data from this system will not be used directly, but rather the diagnosis from the MINI is copied into the Electronisch Patient File.

The SCID-II PQ is scored on paper. The scoring sheet is kept in a locked closet and only contains the patient number as an identifier for the patient.

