**Study design:** A 2-year randomized controlled clinical trial on the effectiveness of feedback interventions for therapists

**Study population:** The study population consists of psychiatric patients between 18 and 65 years that apply for outpatient individual psychiatric treatment in one of the three participating treatment facilities. Patients with psychotic disorders, a current crisis, a high risk of decompensation, a current severe manic episode or insufficient mastery of the Dutch language in reading and speaking are excluded from participating in the study. Patients can have supplement treatments beside the individual treatment and stay in the study, as long as

the individual treatment remains the main treatment. Patients are excluded from the study if individual treatment is not their main treatment.

**Intervention (if applicable)**: The intervention consists of providing feedback to therapists on their patients' progress. In the outcome monitoring feedback condition the therapist gets feedback on patient progress in progress charts and tables. The progress of the patient can be viewed by the therapist at all times, by logging on to the feedback system (RequestXL), but is also actively provided by e-mail at session 1, 3, 5, 10 and 15.

In the complex feedback condition with prediction model the actual treatment course (based on the OQ scores) of the patient is compared with the predicted treatment course. The expected treatment course is calculated by a formula. The progress of the patient can be viewed by the therapist at all times, by logging on to the feedback system (RequestXL), but is also actively provided by e-mail when the patient is not progressing well. The therapist then receives an e-mail with high urgency.

In the complex feedback condition feedback is also provided on the ASC. The ASC is administered when the patient goes off track (through the 75% negative bound of the confidence interval around the predicted treatment course) and measures the therapeutic alliance, motivation, social support and life events. The ASC is combined with so called Clinical Support Tools, a set of Microsoft Word documents that provide practical tips on improving the therapeutic alliance, motivation and social support. The practical tips are based on a literature review on these topics.

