#### 6.2 Randomisation, blinding and treatment allocation

Patients are randomly assigned to one of the three research conditions. The randomization procedure is build in the software used to provide feedback and is completely random. The researcher is aware of the treatment condition of the patients, but cannot influence it. By the nature of the intervention, therapists are aware of the research condition of their patients.

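### Recruiting staff may add and erase patients in the software that draws the condition, with no lock, log or retained first allocation stated, so the integrity of allocation is not secured

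*Protocol*

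**What the plan says.** On randomisation, Protocol 6.2 states: "The randomization procedure is build in the software used to provide feedback and is completely random". The Summary identifies that software, since therapists view progress "by logging on to the feedback system (RequestXL". Section 10.1 names it again as the main data system: "Most of the data is collected through the web-based software RequestXL, which is hosted online through a secure server".

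On access, 10.1 states: "Research assistants have access to all patients in their own research location". It continues: "They can add new patients, erase patients and adapt patient information (not questionnaires". The parenthesis limits what may be adapted. It does not say what becomes of the questionnaires of an erased patient, and no condition is attached to adding or erasing.

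On recruitment, 9.2 says that eligible patients "are contacted a week later by one of the research assistants or the researcher", to be asked whether they will take part.

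On protection of the allocation, 6.2 offers one sentence: "The researcher is aware of the treatment condition of the patients, but cannot influence it". Research assistants are not mentioned there. The same section says that therapists know their patients' condition.

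On retention, 10.1 states: "After study termination the data stored in Request XL will be cleared and deleted". Patient numbers are also to be taken out of the data file once matching is complete.

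**The concern.** The people who bring patients into the trial hold, in the system that allocates them, a right to remove those patients again. Two things could follow.

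- A randomised patient could be erased. Section 6.5 keeps data up to withdrawal in the analysis, and the Summary (main study parameters) counts on data from all patients, drop-outs included. Erasure bypasses both.
- An erased patient might be entered again and receive a second draw.

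Either would damage the randomised comparison if it depended on both the condition and the prognosis. A motive is foreseeable. Section 9.3 tells staff that at-risk patients do much better when feedback is used, and 5.1 lets each therapist have patients in all three conditions, so therapists see who receives none. Nobody need act in bad faith: tidying away a patient who proved unsuitable after the draw has the same effect. Adjustment for initial OQ-45 (8.2) removes only the part of the selection that this score captures.

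**Working it through.** The protocol gives no figure on this point to reproduce. The check is a comparison of passages, followed by an illustration of size.

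**Passages side by side**

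| Question | What the protocol states |
|---|---|
| Where is the condition drawn? | In the feedback software (6.2), which is RequestXL (Summary, 10.1) |
| Who may add and erase there? | Research assistants, for their own location (10.1) |
| Do they recruit? | Yes, together with the researcher (9.2) |
| Is erasure limited to before the draw? | Not stated |
| Is there a lock, a log or a retained first allocation? | Not stated |
| When is the condition drawn? | Not stated |
| Does re-entry trigger a new draw? | Not stated; 10.1 speaks of adding new patients |
| Do assistants see the condition? | Not stated; the researcher and therapists know it (6.2) |

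The erase right is explicit. The redraw, and the assistants' knowledge of the condition, are inferences.

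**Size, under assumptions**

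From the document: target N = 600 and a small effect of d = 0.30 (4.4). Assumed: allocation 1:1:1 (the ratio is not stated), so 600/3 = 200 per arm; arm means of 0 before any change; 10 control patients affected, each 1 SD worse than average; unadjusted means.

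1. Erased only. Control mean: -10/190 = -0.053 SD. Feedback arms unchanged. Spurious difference 0.053 SD.
2. Erased and redrawn once. A redraw returns control one time in three, so on average 10 × 2/3 = 6.67 patients move, 3.33 to each feedback arm. Control: -6.67/193.33 = -0.034. Each feedback arm: +3.33/203.33 = +0.016. Difference 0.051 SD.
3. All 10 end in feedback arms, 5 in each. Control: -10/190 = -0.053. Each feedback arm: +5/205 = +0.024. Difference 0.077 SD. On a single redraw the chance that all 10 leave control is (2/3)^10 = 1.7%, so this case needs repeated redraws and is an upper value for 10 patients.

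Against d = 0.30, these are 0.053/0.30 = 18%, 0.051/0.30 = 17% and 0.077/0.30 = 26%.

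Case 3 with other numbers moved: 4 patients give 4/196 + 2/202 = 0.030 SD; 20 patients give 20/180 + 10/210 = 0.159 SD.

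**Direction.** Worse patients leave control, so control looks better and the bias is against feedback. For the comparison of the two feedback arms it is zero in case 1, and zero in cases 2 and 3 if the moved patients split evenly.

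**Would arm counts reveal it?** The SD of an arm count is sqrt(600 × 1/3 × 2/3) = 11.5. Suppose that, for a fraction f of patients, an unwanted allocation is redrawn once. The expected size of that arm is then 600 × [(1 - f)/3 + f/9].

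| f | Expected size | SDs below 200 |
|---|---|---|
| 5% | 193 | 0.6 |
| 10% | 187 | 1.2 |
| 20% | 173 | 2.3 |

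Up to about 10%, the counts would look ordinary.

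**The case against.** A reader might infer that 10.1 proves the assurance in 6.2 false. It does not. That assurance is about the researcher, 9.2 and 10.1 treat researcher and research assistant as separate roles, and the add and erase rights go only to assistants. Section 6.2 is silent on assistants, which is a gap and not a contradiction.

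A reader might also infer that an unwanted allocation can simply be redrawn. The text does not establish this. It does not say that re-entry produces a new draw or that assistants see the condition. Therapists know the condition but are given no right to add or erase. The route would need a view right that is not described, or a request from someone who knows the condition.

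The protocol also has rules that point the other way. Sections 6.4 and 6.5 handle patients who no longer fit as withdrawals with data kept, and 5.2 does the same when individual treatment stops being the main one. Nor would every trace disappear when RequestXL is cleared: signed consent forms, paper SCID-II sheets with the patient number and diagnoses in the patient file lie outside it, and 10.3 reports inclusion numbers yearly. Reconciling these could reveal a missing participant.

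All of this stands, and it limits the claim. It does not close the gap. The withdrawal rules say what should happen, while the access rights permit something else. The outside records could show a missing patient but not a second draw. An unseen statistical analysis plan would not normally set user rights in the randomisation system.

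**Conclusion.** The point holds as a gap in protection. Assistants who recruit have an unrestricted right to add and erase in the software that allocates, and the protocol states no lock, log or retained first allocation. Removal of a randomised patient is possible under the stated rights and would run against 6.5 and the Summary. A second draw is possible but not established. That allocation has been or will be influenced is not shown, and that no audit log exists is not shown either.

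The size is illustrative and rests on assumed inputs: 200 per arm, 10 control patients, each 1 SD worse. On those inputs the bias against feedback is about 0.05 SD, at most 0.08 SD, before adjustment for initial OQ-45. It concerns feedback against control. For the second primary question, which compares the two feedback forms, it is zero unless the moved patients divide unevenly between them. The case for change is that the remedy is cheap and that a lost or redrawn allocation cannot be repaired in the analysis.

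**What to change.** - **Section 10.1:** remove the erase right once a condition has been drawn. From then on allow only marking a patient as withdrawn, with date and reason.
- **Section 6.2:** state that the condition is drawn after consent and eligibility are recorded, and that a patient who is entered again keeps the first condition.
- **Before RequestXL is cleared:** export the list of all draws (study code, location, date and time, condition, status) and reconcile it with the analysed patients. Keep it in a form consistent with the planned removal of patient numbers, for example under a study code after reconciliation.

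Delaying the draw until the first OQ-45 has been submitted is optional and not needed to close the gap.

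Cost: a change of user rights and of the draw step in a module that was already built for the study, and one extra export. Data-entry mistakes made after the draw stay visible as voided records.

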## **10.2 Amendments**

Amendments are changes made to the research after a favourable opinion by the accredited METC has been given. All substantial amendments will be notified to the METC and to the competent authority. Non-substantial amendments will not be notified to the accredited METC and the competent authority, but will be recorded and filed by the sponsor.

## 10.3 Annual progress report

The sponsor/investigator will submit a summary of the progress of the trial to the accredited METC once a year. Information will be provided on the date of inclusion of the first subject, numbers of subjects included and numbers of subjects that have completed the trial, serious adverse events/ serious adverse reactions, other problems, and amendments.

## 10.4 End of study report

The investigator will notify the accredited METC of the end of the study within a period of 8 weeks. The end of the study is defined as the last patient's last six-months follow-up measure with the OQ-45. In case the study is ended prematurely, the investigator will notify the accredited METC, including the reasons for the premature termination. Within one year after the end of the study, the investigator/sponsor will submit a final study report with the results of the study, including any publications/abstracts of the study, to the accredited METC.

## 10.5 Public disclosure and publication policy

Results will be published in an international peer reviewed journal, as well as in a national journal. In addition, in both participating mental health care organizations the final report will be distributed and results will be presented to the participating therapists. Patients will be informed through the patient newsletter, for which they can subscribe.

